### **Associated Areas of Functioning**

- Deployment Risk and Resiliency Inventory-2 (DRRI-2): The DRRI-2 (Vogt et al., 2012) is a suite of 17 individual scales that assess key deployment-related risk and resilience factors with demonstrated implications for Veterans' long-term health. The following subscales will be used to assess deployment factors: Combat Experiences. We will use the Post-Deployment Life Events and Support scales to evaluate post-deployment factors for Veterans.
- CNS Vital Signs Cognitive Testing: A battery of two tests (Stroop & Shifting Attention) will assess neurocognitive functions.

**Compensation:** Participants will be compensated \$50 for the baseline visit, \$50 for each imaging visit, \$40 for each completed weekly visit, and \$75 for completing each of the follow-up visits. They will be given a \$25 bonus if the baseline/first visit is attended as scheduled. Participants who previously consented to the optional neuropeptide Y will receive \$15 compensation for completing the second blood draw. Thus, participants may receive up to \$755 for completing all visits. Compensation is available in the form of cash, gift card, or check.

Telehealth participants will be offered compensation for travel to and from the three mandatory in-person visits (Baseline, Week 4, & Week 8).

**Neuroimaging Component:** Given the severe negative outcomes associated with co-occurring AUD/SUD and PTSD and lack of effective treatments, investigation of the neural circuitry and neurochemistry underlying AUD/SUD/PTSD and involved in positive therapeutic response could be important in guiding future treatment development studies. To that end, fMRI and H-MRS data will be acquired at baseline and end of treatment on a subset (n=40) of participants to examine (a) glutamate concentrations, (b) resting state connectivity, and (c) response to alcohol/drug, trauma, and neutral cues. Scans will be conducted at the MUSC Center for Biomedical Imaging.

The neuroimaging component will involve three visits, each lasting 60-90 minutes. During visit 1, we will develop the personalized imagery scripts for alcohol/drug, trauma, and neutral cues. During visit 2 (pre-treatment) and visit 3 (end of treatment), we will conduct the fMRI and H-MRS scanning procedures. Imagery scripts will be similar to those developed according to standardized procedures (Sinha & Li, 2007) and employed in our ongoing research.

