Upon arrival to the imaging facility (Center for Biomedical Imaging), participants will first participate in a mock scanning session to acclimate to the MRI scanner and to practice using the joystick before completing the actual MRI scan. After mock scanning, participants will be screened for metal using a handheld metal detector. Trained staff will position individuals on the scanner bed with foam padding placed around their head to prevent motion. Participants will wear ear buds to listen to the audio-recorded scripts. For co-registration and normalization of functional images, a high resolution T1-weighted MPRAGE anatomical image will be acquired with the following parameters: TR = 2300ms, TE = 2.26ms, flip angle = 8°, field of view = 256mm, slice thickness 1.0mm. The scanning planes will be oriented parallel to the anterior commissure–posterior commissure line. The ACC voxel for H-MRS will be placed on midsagittal T1-weighted images, anterior to the genu of the corpus callosum, with the ventral edge of the voxel aligned with the dorsal edge of the genu and a voxel size of 3 x 2.5 x 2.5cm.

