## Protocol: Glial Regulators for Testing Comorbid Posttraumatic Stress Disorder and Substance Use Disorders

Following auto-shimming, single-voxel water-suppressed  $^1\text{H}$ -MRS spectra will be acquired using a Point Resolved Spectroscopy (PRESS) sequence: Repetition Time (RT) = 2000ms; Echo Time (TE) = 40ms; number of averages = 128; an unsuppressed water spectrum will be co-acquired (TE = 40ms, number of averages = 16), scaled for partial volume effects and relaxation, and used as a concentration reference (Mullins et al., 2008).

Participants will be asked to relax and keep their eyes opened and fixed on a cross-hair for two six-minute runs while resting state data are collected. Following this, participants will be exposed to alcohol/drug, trauma and neutral cues, which will be audio recorded descriptions of the most recent time they used alcohol/drug, details of a traumatic event, and details about a relaxing event.

We will use a block design consisting of a single run in which 4 task blocks alternate with rest blocks. The 4 task blocks consist of a neutral cue followed by a trauma cue followed by a neutral cue then an alcohol/drug cue. To minimize potential carry-over effects, the order of task blocks will be counterbalanced so that half of the subjects in the placebo group and half of the subjects in the NAC group are exposed to the alcohol/drug cue first and the remaining participants in each group are exposed to the trauma cue first. This order will be repeated at the end of treatment scan. T2\*-weighted gradient-echo planar images (EPI) will be acquired with the following parameters: TR = 1100ms, TE = 30ms, flip angle =  $65^\circ$ , matrix 64 x 64, field of view = 192mm, slice thickness = 3.0mm, with 48 slices to cover the entire brain.

**Statistical Analyses:** Baseline clinical and demographic characteristics will be collected and contrasts performed between treatment groups. Baseline characteristics found to be significantly associated with primary outcome measures will be included as covariates in the analyses. In general, less than 10% missing data have little impact on power and do not introduce bias, regardless of the missing data mechanism. If the percent missing data are greater than 10%, propensity score methods will be used for data imputation.

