We plan to use REDCap for data capture and management. REDCap (Research Electronic Data Capture) is a software toolset and workflow methodology for electronic collection and management of research and clinical trial data (Harris et al., 2008; Harris et al., 2007). REDCap provides secure, web-based flexible applications, including real time validation rules with automated data type and range checks at the time of entry. Exports are made available for several statistical packages including SPSS, SAS, SATA, R and Microsoft Excel.

**Power and Sample Size Estimation.** It is expected that subjects treated with NAC, as compared to placebo, will exhibit significantly lower PTSD symptoms and craving at week 8. The effect sizes for these analyses ( $d = 1.27$ ,  $d = 1.03$ , respectively) are based on our PoP data. A sample size of 26 would provide power ( $1-\beta$ ) of .80 to detect a large effect size with a Type 1 error protection level of .05 (Cohen, 1988). It is expected that NAC, as compared to placebo, will exhibit significantly lower AUD/SUD severity at week 8. To date, no published studies have examined NAC for the treatment of AUD. Assuming a medium effect size ( $d = .2$ ), with a Type 1 error protection level of .05 and  $(1-\beta) = .80$ , a total sample of 58 would be required. Recent unpublished pilot data conducted by our group examining the effects of NAC vs. placebo on standard number of drinks among patients with cocaine dependence and comorbid AUD ( $n=28$ ) found a statistically significant treatment group effect. With regard to neuroimaging, a recent study of 29 individuals (PTSD=14, controls=15) observed significant differences in PFC-AMY resting state connectivity (Sripada et al., 2012). The effect size for this difference was 0.8 (Cohen's  $d$ ). Thus, power ( $1-\beta$ ) reaches .80 with a total sample size of  $N=26$  (two-tailed,  $\alpha = .05$ ). Another study of 45 cocaine-dependent individuals showed that lower PFC-AMY connectivity at baseline predicted relapse (McHugh et al., 2014). The effect size for this reduction was 1.0. Thus, power ( $1-\beta$ ) reaches .80 with  $N=34$  subjects (two-tailed,  $\alpha = .05$ ).

**Hypotheses:** The hypotheses and statistical approaches for testing each hypothesis are listed below.

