For hypotheses 3A and 3B, the following preprocessing and analytical parameters will be used. Preprocessing: Post-acquisition preprocessing and statistical analysis of imaging data will be performed using FEAT (FMRI Expert Analysis Tool) Version 5.98, part of FSL (FMRIB's Software Library). Data will be preprocessed using scripting tools from FEAT. Non-brain signal will be removed using FSL's BET brain extraction. Scans will be corrected for motion using FSL's linear registration and scans will be spatially smoothed. Participants with head motion  $\geq 0.2$  mm will be excluded from the analyses (Power et al., 2012). Motion artifacts will be identified and scrubbed from each subject's data. Scans will be spatially co-registered with a standardized anatomical template (Montreal Neurological Institute) using a 12 parameter affine transformation. Analysis: Functional connectivity will be measured using a psychophysiological interaction (PPI) seed-based approach (Friston et al., 1997). PPI analysis is used to assess the functional coupling between different brain regions. The PPI is defined as the change in connectivity of one area (i.e., the seed region) to another in relation to the experimental context (e.g., alcohol vs. neutral cues). PPI analyses for resting state, trauma and alcohol/drug cues will be performed separately. Customized sq. wave forms representing the trauma run (1=trauma block and -1=neutral block) and the alcohol/drug cue run (1=alcohol/drug block and -1=neutral block) will be convolved with a double-gamma hemodynamic response function. A mask of the seed region will be made using a 12-mm diameter sphere located in the center of the AMY using the MNI coordinates (x, y, z =  $\pm 22, 0, -22$ ). The transformation parameters described above will also be applied to the mask. For each subject, the mean corrected and high pass filtered time series of the BOLD signal in the AMY will be extracted and used in a single subject whole brain PPI analysis. The PPI model will include the task vector, time series of the BOLD signal in the AMY, a term representing the positive task x seed interaction, and a term representing the negative task x seed interaction. The first level analysis will generate contrast images of the parameter estimates for each of the four regressors. Voxels will be thresholded at  $Z > 2.3$  using a corrected cluster threshold of  $p=0.05$ . The contrast images of the parameter estimates of the positive and negative task x seed interactions will be combined for group-level t-tests to identify regions that exhibited altered connectivity with the AMY during the trauma and alcohol/drug cues as compared to neutral cues. All group-level results will be thresholded at  $Z > 2.3$  using a corrected cluster threshold of  $p=0.05$ . Separate linear regression tests will be used to test for associations between PFC-AMY connectivity at baseline and improvement in AUD/SUD and PTSD symptoms during treatment. Changes in total standard drinks will be

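### The imaging plan excludes participants for head motion of 0.2 mm or more without defining the measure, does not apply the rule by run, and has no motion term in the Hypothesis 3 regressions

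*Combined protocol and SAP*

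**What the plan says.** All references are to the combined protocol and SAP. Under Statistical Analyses, the preprocessing text for Hypotheses 3A and 3B gives three steps for motion. Realignment: "Scans will be corrected for motion using FSL's linear registration and scans will be spatially smoothed". Exclusion of people: "Participants with head motion $\geq 0.2$ mm will be excluded from the analyses". Cleaning of what remains: "Motion artifacts will be identified and scrubbed from each subject's data". A citation is attached to the exclusion rule, but the measure is not written out. No scrubbing threshold and no minimum amount of retained data is given.

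The Neuroimaging Component plans scans "on a subset (n=40) of participants", with "two six-minute runs while resting state data are collected" followed by one cue run that holds the trauma, alcohol/drug and neutral blocks. To limit movement it provides a mock scan and "foam padding placed around their head to prevent motion".

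Connectivity at rest, with trauma cues and with alcohol/drug cues is analysed separately. The hypothesis tests are then regressions: "Separate linear regression tests will be used to test for associations between PFC-AMY connectivity at baseline and improvement". No motion covariate is listed.

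Power and Sample Size Estimation gives N=34 for the study in which connectivity predicted relapse ("The effect size for this reduction was 1.0") and N=26 for a resting-state difference of d=0.8. Neither figure carries an allowance for scans lost to motion.

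**The concern.** This rule decides who enters the Hypothesis 3 analysis, and it leaves three things open.

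First, two analysts could use peak, any-frame or average motion, obtain different samples, and both comply. The choice could also be made after the data are seen.

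Second, the exclusion is worded for the person and the analyses as a whole. Movement in the cue run would then discard usable resting data from the same person. The text also does not say whether movement in the week 8 scan counts against regressions whose predictor is baseline connectivity.

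Third, participants who stay in will still differ in how much they moved. With no motion term, motion-related variation in the connectivity estimate goes straight into the regression. If motion is also related to clinical change, the association is confounded. The documents do not say whether it is; that is a reason to adjust, not evidence of bias.

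At stake is Hypothesis 3, which rests wholly on a subset of 40. Hypotheses 1 and 2 are not affected.

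**Working it through.** **1. The plan's own figure.** Inputs from Power and Sample Size Estimation: d=1.0, two-tailed alpha .05, power .80, N=34. A two-sample t test with equal groups and the noncentral t distribution gives power 0.807 at N=34, so the figure reproduces as a two-group comparison.

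**2. Room for loss.** 40 − 34 = 6, and 6/40 = 15%. Two-group power at d=1.0 by number analysed:

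| n | 40 | 34 | 30 | 20 | 10 |
|---|---|---|---|---|---|
| power | 0.87 | 0.81 | 0.75 | 0.56 | 0.29 |

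The planned test is a regression. With equal groups assumed, r = d/√(d²+4) = 1/√5 = 0.447. By the Fisher z approximation, n = ((1.96+0.8416)/atanh(0.447))² + 3 ≈ 36.9, so 37. On that footing 3 of 40 can be lost.

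The stated N=26 would leave 14 to spare, but it does not reproduce as a total. For d=0.8 the two-sided t test needs 52 in total, which is 26 per group. I therefore do not rely on it.

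**3. Any-frame reading.** Each resting run lasts 360 s. With the repetition time of 1.1 s listed after the cue task, and assumed to apply at rest, 360/1.1 gives 327 whole volumes per run and 654 over two runs. Let p be the chance that a volume reaches 0.2 mm. The documents give no value, so it is varied. With independent volumes, the expected number kept is 40 × (1−p)^654:

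| p per volume | expected kept of 40 |
|---|---|
| 0.01% | 37.5 |
| 0.025% | 34.0 |
| 0.1% | 20.8 |
| 0.2% | 10.8 |
| 0.5% | 1.5 |
| 1% | 0.06 |

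Movement comes in bursts, so independence is a simplification. Counting episodes instead, with a Poisson mean m per person over the 12 minutes that is the same for everyone, the expected number kept is 40 × exp(−m). That is 14.7 at m=1 and 5.4 at m=2. Keeping 34 needs m ≤ −ln(0.85) = 0.16. If episodes were concentrated in a few people, more would be kept. The cue run is not counted.

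**4. Average-motion reading.** Nothing in step 3 applies. The loss would depend on how average motion is distributed across participants, which the documents do not give.

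**5. The two sentences together.** Under the any-frame reading, nobody retained has a volume at or above 0.2 mm, so scrubbing has little left to remove. Under the average reading, a retained participant can still have bad volumes, and scrubbing has a purpose.

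**The case against.** A reader might infer that the cut-off, applied as written, would empty the imaging sample. The documents do not support that. It needs an any-frame reading and a motion rate, and the text supplies neither. The scrubbing sentence points the other way: cleaning the data of retained participants implies that they may have some affected volumes, which fits an average better. On that reading the two sentences form a coherent two-step procedure.

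A reader might also conclude that 0.2 mm is really a tolerance for single volumes, misapplied to people. Nothing in the documents says so, and the cited source is not available here. That the cut-off is small against the 3 mm in-plane voxel (192/64) does not settle it.

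Three further objections carry weight. The mock scan, padding and realignment all reduce the problem, although none defines who is excluded. The plan never calls 34 the minimum analysable sample. And a strict rule set in advance is not an error in itself.

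If the undefined measure were the whole point, this would be a request for missing detail. What goes further is that exclusion is attached to the person although the analyses are separate, and that the regressions do not adjust for motion. Both hold under either reading.

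**Conclusion.** The concern holds as a design weakness in the Hypothesis 3 analysis: the motion measure is undefined, exclusion is not applied by run, and the regressions have no motion term.

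Its size cannot be fixed from the documents. On a peak or any-frame reading much of the subset could go: about 21 of 40 would be kept if 0.1% of resting volumes reached the cut-off, given independent volumes and the same repetition time at rest. On an average reading the loss is unknown and may be small. The firm figure is the margin: 6 of 40 against the stated N=34, or about 3 if d=1.0 is converted to a correlation with equal groups assumed, with no allowance made for motion loss. Emptying of the sample is not shown.

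**What to change.** Amend the preprocessing and regression text for Hypotheses 3A and 3B before the scans are analysed:

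- Define the participant-level criterion as average frame-to-frame displacement above a stated limit, or less than a stated amount of usable data after scrubbing.
- State the volume-level scrubbing threshold separately.
- Apply exclusion by run or by analysis, so that movement in the cue run does not discard usable resting data. Because the trauma and alcohol/drug blocks share one run, state the usable data needed for each cue analysis. Say whether movement in the week 8 scan affects the baseline-predictor regressions.
- Include mean displacement as a covariate in the 3A and 3B regressions.
- Report the number excluded, by arm and by analysis.

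This is a change of wording and needs no new data. The covariate costs one degree of freedom: in a simple regression on 40 participants, the residual falls from 38 to 37. Some participants with moderate motion will stay in, so the result leans partly on that adjustment.

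### The cue scan is one four-block run, but the connectivity model is written for separate trauma and drug-cue runs, and whether the cue-versus-neutral estimate is biased depends on choices the plan leaves open.

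*Combined protocol and SAP*

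**What the plan says.** The Neuroimaging Component describes the cue task as "a single run in which 4 task blocks alternate with rest blocks". On content it says: "The 4 task blocks consist of a neutral cue followed by a trauma cue followed by a neutral cue then an alcohol/drug cue". The cue order is varied within each arm: "half of the subjects in the placebo group and half of the subjects in the NAC group are exposed to the alcohol/drug cue first". Block and rest durations are not given.

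The analysis text for Hypotheses 3A and 3B says that "PPI analyses for resting state, trauma and alcohol/drug cues will be performed separately". It then specifies "Customized sq. wave forms representing the trauma run (1=trauma block and -1=neutral block) and the alcohol/drug cue run", the second coded in the same way, each convolved with a double-gamma response. Each model has four regressors: the task vector, the amygdala time series, "a term representing the positive task x seed interaction, and a term representing the negative task x seed interaction". The positive and negative interaction images are then put together for group-level t-tests, by a rule that is not stated. Clusters that pass the threshold supply the predictors for change in total standard drinks (3A) and change in CAPS-5 (3B).

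**The concern.** Two runs are modelled and one is acquired. The text does not bridge the gap, and three things needed to build the design matrix are missing:

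- how the single run is divided, if it is;
- whether one or both neutral blocks take the value -1 in each vector;
- how the two interaction images are combined.

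If the whole run is used, there are two neutral blocks to one trauma block, with rest at 0. A single +1/-1 vector is then unbalanced and cannot fit a response that trauma and neutral cues share. The alcohol/drug block has no regressor and falls into the baseline with rest. The quantity labelled trauma versus neutral could then carry some general response to hearing any script. The drug-versus-neutral estimate has the same problem. These estimates choose the clusters and become the predictors in 3A and 3B.

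**Working it through.** The plan gives no figure to reproduce, so the check is on the design matrix.

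**Block algebra.** Assume equal block lengths, four rest blocks, no haemodynamic lag, both neutrals at -1 and one interaction term. In a PPI the seed term plays the part of the intercept, so the same weights apply to the connectivity slope. The least-squares weight of block i is (x_i - mean)/sum of (x_i - mean)².

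- x = -1, +1, -1, 0, then four zeros for rest. Mean = -1/8 = -0.125. Sum of squares = 3 - 8 × 0.125² = 2.875.
- Weights: trauma 1.125/2.875 = 0.391; each neutral -0.875/2.875 = -0.304; drug 0.125/2.875 = 0.043; rest 4 × 0.043 = 0.174 in total.
- A response of 1 to every cue and 0 at rest gives 0.391 - 0.609 + 0.043 = -0.174. From -1 to +1 is two units, so trauma minus neutral is 2 × -0.174 = -0.35 when the true difference is 0. With three or five rest blocks the coefficient is -0.150 or -0.192, that is -0.30 or -0.38.
- A response to the drug cue alone gives 2 × 0.043 = +0.09.
- With only one neutral at -1, the mean is 0 and the weights are +0.5 and -0.5. The shared response cancels to 0.
- With both neutrals at -1 and a drug term added, seven blocks remain. The mean is -1/7, the sum of squares is 3 - 1/7 = 20/7, and the shared response gives 2 × (-1 + 3/7)/(20/7) = -0.40. Modelling the other cue alone does not cure the problem.

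**Simulation.** Inputs from the plan are TR 1.1 s, the double-gamma response and both cue orders. Assumed inputs are block/rest lengths of 60/60, 120/60 and 60/20 s and illustrative effect sizes, with 400 replicates per order and scenario. The entries are bias in trauma minus neutral, as a fraction of a unit effect, with the true connectivity difference at 0.

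| Reading of the model | All cues raise connectivity | Only drug cue raises it | All cues co-activate seed and target |
|---|---|---|---|
| Both neutrals -1, one interaction | -0.21 to -0.39 | +0.08 to +0.14 | about +0.09 |
| Both neutrals -1, two interactions, differenced | about 0 | about 0 | +0.04 to +0.12 |
| One neutral per cue, or two half-runs | about 0 | about 0 | about 0 |
| First row plus drug regressor and drug interaction | -0.26 to -0.44 | about 0 | about +0.09 |
| Separate trauma, neutral and drug regressors and interactions | 0.01 or less | 0.01 or less | 0.01 or less |

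A second set of simulations put the co-activation residue in the second row at +0.07 to +0.18. One limit applies to the third row. If the trauma and drug cues co-activate the two regions but neutral does not, those versions left +0.08 to +0.17, while the last row stayed within 0.01.

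The rule for combining the images also matters. Taken alone, the positive interaction absorbs the general response (+0.63 to +0.84). If the negative term is only the sign-reversed product, the design has rank 4 with 5 columns (four regressors and an intercept).

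**Effect on 3A and 3B.** Write a participant's estimate as t + b·g, where t is the true difference, g the general cue response and b the bias per unit of it. If g is the same for everyone, b·g is a constant and the slope of outcome on estimate does not change. The slope can change only if g varies between people. Separately, a non-zero mean of b·g shifts the group t-tests, and so which clusters pass Z > 2.3 with the corrected cluster threshold.

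**The case against.** The best defence is that the text can be read harmlessly. It codes a trauma block against a neutral block in the singular, each cue is preceded by its own neutral block, and the analyses are done separately. One neutral paired with each cue, or the run cut into two neutral/cue segments, is therefore a natural reading, and a general cue response then causes about 0 bias. If the run is cut, the other cue is not in the data at all. Separate positive and negative interactions, if differenced, also remove the connectivity bias. All of this stands. It shows that bias is not inevitable, but the plan commits to none of these readings.

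A reader might infer three stronger things that the documents do not support:

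- That the planned estimate is biased by a definite amount. On the algebra above, the shared response is 0.174/0.391 = 44% of what a true one-unit trauma effect would give. That needs both neutrals at -1 and a single interaction, whereas the plan lists two interaction terms.
- That the unmodelled cue is the main fault. Its weight is only 0.043, and adding terms for it leaves -0.26 to -0.44. The unbalanced single vector is the main source, and the omitted cue adds to it.
- That the tests of 3A and 3B are invalid. A constant offset leaves their slopes unchanged.

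**Conclusion.** The acquisition and analysis texts contradict each other, and the first-level model cannot be built from the plan without choices that it does not record. The size of the problem is conditional:

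- about -0.2 to -0.4 of a unit effect from a general cue response, with both neutrals at -1 and one interaction;
- about 0 for connectivity but roughly +0.04 to +0.18 from general co-activation, with two differenced interactions;
- about 0 from a general cue response, with paired neutrals or half-runs.

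These figures rest on assumed block and rest lengths and illustrative effect sizes. The harm to 3A and 3B would come through cluster selection at the group threshold and through between-person differences in general cue response. Neither has been quantified. Only the cue-based connectivity estimates in the imaging subset (n=40) are touched. Hypotheses 1 and 2 and the resting-state part of Hypothesis 3 are not. This should be settled before the imaging data are analysed.

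**What to change.** Reconcile the two sections by fitting one first-level model to the single cue run:

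- separate task regressors for trauma, alcohol/drug and neutral (both blocks);
- the amygdala time series;
- a seed interaction for each of the three conditions.

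Test trauma minus neutral and alcohol/drug minus neutral as contrasts of the interaction terms, carry those contrasts to the group level, and drop the positive and negative interaction terms. The model then has 3 + 1 + 3 = 7 regressors in place of 4. The cost is SAP wording, a change to the analysis script and three more regressors per participant. No extra scanning is needed.

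### The Hypothesis 3A/3B connectivity models have no term for breathing and pulse signal shared by amygdala and prefrontal voxels, and the resting model is not defined

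*Combined protocol and SAP*

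**What the plan says.** All of this stands in the combined protocol and SAP, in the analysis text for Hypotheses 3A and 3B and under Neuroimaging Component.

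- **Model.** "The PPI model will include the task vector, time series of the BOLD signal in the AMY", and then "a term representing the positive task x seed interaction, and a term representing the negative task x seed interaction". The first level is to produce "contrast images of the parameter estimates for each of the four regressors".
- **Seed.** For each participant, "the mean corrected and high pass filtered time series of the BOLD signal in the AMY will be extracted". No filter cut-off is given, and no low-pass or band-pass filter is mentioned.
- **Cleaning.** "Non-brain signal will be removed using FSL's BET brain extraction". Scans are realigned and smoothed, participants with head motion of 0.2 mm or more are excluded, and "Motion artifacts will be identified and scrubbed from each subject's data".
- **Acquisition.** The EPI settings are "TR = 1100ms, TE = 30ms, flip angle" of 65 degrees. Rest is two six-minute runs. For registration, "a high resolution T1-weighted MPRAGE anatomical image will be acquired".
- **Use.** The PPI approach is applied separately to rest, trauma cues and alcohol/drug cues. The parameter estimate at the centre of each significant cluster is the predictor for change in total drinks (3A) or CAPS-5 (3B). The imaging subset is 40 participants.

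Neither section describes a white-matter, CSF or global regressor, a component-based correction, or a cardiac or respiratory recording in the scanner. Pulse appears only among the vital signs.

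**The concern.** Breathing and heartbeat produce fluctuations in many brain voxels at once. If the same fluctuation reaches the amygdala seed and a prefrontal voxel, a regression of one on the other gives a positive slope without any neural coupling. Participants differ in how strongly they carry this signal. The person-level predictor in Hypothesis 3 would then mix coupling with physiology.

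Two consequences are possible. The added between-person noise weakens a true association and lowers power in a sample of 40. If physiological loading is itself related to symptom change, for instance through arousal, it can also create an association that is not about prefrontal-amygdala coupling.

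There is also a gap of definition. The four-term list contains a task vector and two task products, so it can describe only the cue models. The resting regressors are never stated.

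**Working it through.** **1. The plan's own count.** Task (1) + seed (1) + positive and negative interaction (2) = 4, which agrees with the stated four. None of these is a confound term.

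**2. What the cleaning steps cover.** Brain extraction removes tissue outside the brain, not fluctuation inside it. Realignment, exclusion and scrubbing address movement. The high-pass filter removes slow drift.

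**3. Frequencies.** The sampling rate is 1/1.1 = 0.909 Hz and the Nyquist limit is 1/(2 × 1.1) = 0.4545 Hz. It is assumed here that the 1.1 s TR also applies at rest.
- Breathing, assumed at 0.2–0.3 Hz, lies below Nyquist, in a range that a high-pass filter keeps.
- Pulse at f appears at |f − 0.909|. Assumed rates of 0.95, 1.0, 1.1 and 1.2 Hz alias to 0.041, 0.091, 0.191 and 0.291 Hz.

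**4. Rest, zero true coupling.** Let a share s of the variance in both seed and target be common physiological signal. The expected seed slope is then s. One run has 360/1.1 ≈ 327 volumes. Simulated with white noise:

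| s (assumed) | mean slope | P(Z > 2.3) |
|---|---|---|
| 0 | 0.00 | 0.9% |
| 0.05 | 0.05 | 7.5% |
| 0.10 | 0.10 | 31% |
| 0.20 | 0.20 | 92% |

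These are rates for a single pair of series, not the plan's cluster-corrected group error rate.

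**5. Rest, effect on Hypothesis 3.** Assumed model: seed = neural + L × p; target = b × neural + L × p + noise, with unit variances. The expected slope is (b + L²)/(1 + L²). With b = .3:
- L = .6 gives (.3 + .36)/1.36 = .485. Moving L from .45 to .75 moves the slope from .418 to .552.
- L = .3 gives (.3 + .09)/1.09 = .358. Moving L from .25 to .35 moves it only from .341 to .376.

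Simulation inputs, all assumed unless noted: n=40 (plan); b with mean .3 and SD .15; 200 effective time points; a tissue regressor that measures p with noise SD .5 against signal SD 1; outcome correlation with true coupling r = d/√(d² + 4) = 1/√5 = .447, from the plan's d = 1.0. False support means that the outcome is unrelated to b and correlates .3 with L.

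| L mean, SD | power as planned | power with tissue regressor | false support as planned | false support with regressor |
|---|---|---|---|---|
| .6, .15 | .54 | .72 | 12% | 6% |
| .6, .30 | .45 | .71 | 22% | 8% |
| .6, .45 | .34 | .69 | 28% | 9% |
| .3, .05 | .74 | .76 | 4.5% | 3.7% |

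Results vary with how the noise is coded. Another implementation of the first three rows gave power of .55/.32/.23 as planned and .69/.65/.60 with the regressor, and false support of 17%/25%/32% against 4%/8%/12%.

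**6. Cue models, zero true coupling.** Let physiological amplitude be k times as large in cue blocks as in neutral blocks. The slope is s in neutral blocks and k²s/(k²s + 1 − s) in cue blocks, and the spurious contrast is the difference. For s = .10 and k = 1.5 this is .225/1.125 − .10 = .10.

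| s | k = 1 | k = 1.5 | k = 2 |
|---|---|---|---|
| .05 | 0 | .06 | .12 |
| .10 | 0 | .10 | .21 |
| .20 | 0 | .16 | .30 |

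Simulation agrees (.13 in place of .12 in the first row). Imperfect tissue regressors without task products cut these contrasts to about .05 or less. Adding the products cut them to about .02 or less.

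**The case against.** **The four may be only the effects of interest.** Contrast images are not normally made for nuisance terms, so the design matrix could hold more. This is fair as a reading of intent. But the text that sets out the preprocessing and analysis parameters mentions no such term, so the wording needs changing either way.

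**The power figures are for a model the plan does not state.** They use a resting regression of target on seed, whereas the four-term list fits only the cue models. This stands. It is why the missing resting definition is part of the point, and why the cue models are worked separately.

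**The harm under cues is conditional.** This stands. The seed main effect absorbs shared signal of constant amplitude, and the bias is zero at k = 1. The documents give no value for k. A difference is plausible because trauma and drug scripts are compared with a relaxing event, but it is not shown.

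**The direction of benefit depends on the assumptions.** This also stands. If the tissue series carries neural signal with weight 0.3 (loading mean .3), one simulation gave power falling from .68 to .63 (SD .15) and from .70 to .66 (SD .10). The reversal is small and depends on how the leakage is modelled: it appears when the tissue series picks up both seed and target signal, and not generally when it picks up one.

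A reader might infer that breathing and pulse do distort the predictor, or that no Hypothesis 3 result, positive or null, could be read as concerning coupling. The documents do not support that. They give no physiological variance share, loading or amplitude ratio, and at low loading the effect is negligible.

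**Conclusion.** The omission is established from the text: no physiological term is described for the cue models, the resting model is undefined, and the listed cleaning steps do not remove breathing or aliased pulse. At rest, shared physiological signal passes directly into the predictor. Under cues it does so only where fluctuation differs between block types.

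The consequence cannot be sized from the documents. Under the assumptions shown, it runs from almost nothing to a loss of about half the power (.34 against .69) and false support of 28% against 9%. The false-support figures also need the assumed .3 correlation between physiology and outcome.

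The point concerns a mechanistic hypothesis in a subset of 40. The NAC-placebo comparisons on drinking, craving and CAPS-5 are untouched. It should be corrected because the correction costs little and prespecifying it stops denoising choices from being made after outcomes are seen.

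**What to change.** In the analysis text for Hypotheses 3A and 3B:

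1. State the resting model explicitly: amygdala seed plus confounds, with no task terms.
2. Add the mean white-matter and mean CSF time series as confound regressors in every first-level model (rest, trauma, alcohol/drug). Take the masks from a segmentation of the T1 image already acquired, and filter the series as the data are filtered.
3. State that the parameter estimates used in the Hypothesis 3 regressions come from these models.
4. Optionally, add tissue-by-task products in the cue models as a sensitivity analysis. They should not be in the main model by default: the cue data are one run with four task blocks, and these products may be collinear with the seed-by-task terms.

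The cost is SAP wording, a small amount of processing with no new data, and two degrees of freedom of about 327 volumes per resting run (more in the cue sensitivity analysis). A little true shared signal may be removed, and the tissue regressors reduce the physiological contribution without eliminating it.
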